9.4.2.4 Subgroup analyses

Subgroup analyses for the primary endpoint will be performed for the following subgroups:

- diabetics and non-diabetics at baseline
- CKD1, CKD2, and CKD3+CKD4 at baseline
- Microalbuminuria and macroalbuminuria at baseline
- <Median baseline sUA and ≥ median baseline sUA
- Baseline NT-proBNP < 360 pg/mL and NT-proBNP ≥360 pg/mL
- Baseline eGFR ≤60 mL/min/1.73 m² vs >60 mL/min/1.73 m²
- · Race of Black or African American, White, Asian, Other
- Age <65, and ≥65 years

- Gender of male, female
- Geographic region

The primary analysis model will be repeated for each subgroup adding factors for subgroup and treatment by subgroup interaction.

These analyses will be conducted only to the extent the results are considered reliable, eg, the analyses should converge.

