4.1.2.3 Week 0 (Visit 3)

- Collect first morning void samples from 3 days before visit (for primary CCI biomarkers)
- Review demography information
- Update concomitant medication
- Record medically important events as medical history
- Perform brief PE
- Record vital signs
- Record weight
- Obtain electrocardiogram (ECG)
- Obtain blood samples for clinical chemistry and haematology, efficacy assessments (s-UA, creatinine, eGFR, Cystatin C, NT-proBNP).
- Genetics sampling for some patients
- · Obtain urine samples for safety assessment (dipstick urinalysis
- Conduct renal MRI and PWV evaluation for patients who consented to participate in MRI sub-study prior to randomisation
- Reactive hyperaemia evaluation

- Perform pregnancy urine dipstick test for women of childbearing potential; after 2 positive urine tests, a serum pregnancy test is to be done by central laboratory
- Review inclusion/exclusion criteria
- Randomise patients via IVRS/IWRS transaction
- Dispense titration Step-1 dose
- Dispense containers for morning voids

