9.4.2.1 Primary efficacy analysis

The primary efficacy variable is the change from baseline in UACR at 6 months (Week 34, ie, 26 weeks of treatment following an 8-week titration phase). Primary analyses will be performed on the FAS population, which consists of all randomised patients regardless of

treatment discontinuation. In other words, post-discontinuation data will be collected and included in the primary analysis. Details on how to handle missing data will be provided in the SAP.

In addition to analysis of the hypotheses in Section 9.1, the primary efficacy variable will be analysed comparing (initial dosing regimen):

- Intermediate dose verinurad plus allopurinol with placebo
- Low dose verinurad plus allopurinol with placebo
- High dose verinurad plus allopurinol with allopurinol alone
- Intermediate dose verinurad plus allopurinol with allopurinol alone
- Low dose verinurad plus allopurinol with allopurinol alone

The analysis of change in UACR from baseline to Week 34 will be conducted on the natural log-transformed UACR values using a repeated measures mixed model.

The analysis model will include the fixed categorical effects of treatment, week, DM status yes or no, microalbuminuria or macroalbuminuria, NT-proBNP < or \geq 360 pg/mL, use of SGLT2 yes or no, and treatment-by-week interaction as well as the continuous fixed covariates of baseline log(UACR) and baseline log(UACR) by-week interaction. An unstructured matrix for the within patient error variance-covariance will be used. The denominator degrees of freedom will be calculated according to the Kenward-Roger method. A number of back-up models will be defined in the SAP in case of non-convergence of the preferred model or other issues.

The least squared mean change from baseline to 6 months in the log-transformed UACR will be calculated by treatment with its 95% confidence intervals. The least squared mean difference between the treatments will be calculated with its 95% confidence interval. P-values of the treatment differences between active treatment group and placebo/comparator will also be calculated.

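### The protocol assesses effect modification by continuous baseline measures only through categories, with sUA cut at the sample median; a treatment-by-continuous-baseline term should be added

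*Supplement*

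**What the plan says.** Section 9.4.2.4 lists ten subgroup factors for the primary endpoint. Those that come from a continuous measure are:

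- sUA: "<Median baseline sUA and ≥ median baseline sUA"
- eGFR, twice: "CKD1, CKD2, and CKD3+CKD4 at baseline" and "Baseline eGFR ≤60 mL/min/1.73 m² vs >60 mL/min/1.73 m²"
- NT-proBNP: "Baseline NT-proBNP < 360 pg/mL and NT-proBNP ≥360 pg/mL"
- age: "Age <65, and ≥65 years"
- albuminuria: micro against macro

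The method is stated there: "The primary analysis model will be repeated for each subgroup adding factors for subgroup and treatment by subgroup interaction". The section limits these analyses to those giving reliable results, for example models that converge. It does not pass the modelling to the SAP, whereas Section 9.4.2.1 does so for missing data and Section 9.4.2.2 for dose response.

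The primary model in Section 9.4.2.1 carries "continuous fixed covariates of baseline log(UACR) and baseline log(UACR) by-week interaction". Neither term involves treatment, and baseline sUA is not in the model.

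At Week 0, before randomisation, Section 4.1.2.3 collects blood for "efficacy assessments (s-UA, creatinine, eGFR, Cystatin C, NT-proBNP", together with first morning void urine for UACR. Age comes from the demography taken at screening.

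**The concern.** Cutting a continuous modifier into groups treats a patient just above the cut like one far above it. If the treatment effect changes gradually with baseline sUA, the interaction test loses power. The output is then a contrast between two groups, not an estimate of how the UACR effect changes per mg/dL. The sUA cut also has no value in mg/dL until the sample is known.

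This matters most for sUA. The trial asks whether intensive urate lowering helps the kidney (Section 2.1) and enrols on sUA of at least 6 mg/dL. Whether patients with higher urate gain more is therefore a natural question for a Phase 2b study that may guide selection for a later trial. Interaction tests are already weak at this sample size, and the grouping weakens them further.

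**Working it through.** **Inputs from the documents.** 145 per arm, log-scale SD 1.0, planned difference 0.29 (25% reduction), two-sided alpha 0.10, 80% power (Section 9.2); sUA at least 6 mg/dL (Section 5.1.1).

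**Assumed.** A linear interaction, the sUA distribution, and alpha 0.10 for the interaction test. The documents state none of these, and give no power for subgroup tests.

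**1. The plan's own figure.**
- SE of a two-arm difference = sqrt(2/145) = 0.117.
- Power = Φ(0.29/0.117 − 1.645) = 79.5%; with ln(0.75) = −0.288 it is 79.0%.
- The stated 80% is reproduced.

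**2. Information kept by a median split.** For a linear interaction, the relative efficiency of the split against the continuous term is the squared correlation between the modifier and its above-median indicator. For a normal modifier this is 2/π = 0.637, a loss of 36.3%. To make up the loss would take π/2 = 1.57 times the patients.

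| Assumed sUA shape | Loss |
|---|---|
| Normal, not truncated | 36% |
| Normal truncated at 6 mg/dL (underlying mean 6–8, SD 1–2) | 34–38% |
| Lognormal truncated at 6 mg/dL (underlying median 7.5, log SD 0.15–0.30) | 37–44% |
| Uniform | 25% |
| Exponential | 52% |

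An off-centre cut keeps φ(z)²/[p(1−p)] for a normal modifier, where p is the share below the cut. That is 58% at the 30th percentile and 49% at the 20th. This bears on the fixed cuts for eGFR, NT-proBNP and age, whose position in the sample is unknown.

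**3. Power of the interaction test, high dose against placebo.**
- Continuous term: SE of the slope per SD = sqrt(2/145) = 0.117.
- Median split: the expected contrast is 1.596 × slope, and its SE is sqrt(8/145) = 0.235.
- At a slope of 0.29 per SD (effect nil at one SD below the mean, doubled at one SD above): z = 0.29/0.117 = 2.47 for the continuous term and 1.596 × 0.29/0.235 = 1.97 for the split. Power is about 79% against 63%.
- At a slope of 0.20 per SD: about 52% against 39%.
- Starting from exactly 80% on the continuous scale: Φ(2.487 × sqrt(0.637) − 1.645) = 63%. With 25% loss it is 69%; with 50% loss, 54.5%.

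**4. Simulation.** In 4,000 two-arm trials of 145 per arm with a normal modifier and slope 0.292, the interaction was detected in 78.5% with the continuous term and 61.8% with the median split.

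**The case against.** The strongest reply is that Section 9.4 calls itself a summary and the SAP is not shown. The numbering also goes from 9.4.2.2 to 9.4.2.4, and parts of the endpoint text are blacked out. A reader might infer that the trial tests continuous effect modification nowhere. The documents cannot support that. What stands is that the protocol states a method for subgroups, and that method is categorical.

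Four other strong readings also fail:

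- *All cuts are dichotomies.* CKD stage has three groups, so categorised is the accurate word.
- *Baseline UACR enters the subgroup model only as a category.* The primary model already has continuous log(UACR). Only its interaction with treatment is absent.
- *sUA is the established key modifier.* The documents make sUA the treatment target. That its baseline level modifies the UACR effect is an inference, and it is one of ten listed factors.
- *The eGFR split at 60 is redundant and should go.* It overlaps heavily with the CKD grouping on conventional staging, which the protocol does not spell out. A two-group version can still be useful if the CKD1 cell is small.

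The size of the loss depends on assumptions. A slope that makes the effect nil at −1 SD is a strong interaction, and at 0.20 per SD even the continuous test has only 52% power. The calculation covers one pair of arms with all 145 evaluable, while the planned model has five arms. For a threshold effect, a well-placed cut could do as well or better. An observed median can also be reported and reused, although it is not fixed in advance. These points limit the claim but do not remove the gain when the relation is gradual.

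**Conclusion.** The point holds as a modest one. For sUA, eGFR, NT-proBNP, albuminuria and age, the protocol text shown assesses effect modification through categories only, although the measured values are available. For a roughly linear interaction, the sUA median split loses about 36% of the information if sUA is normal and 34–44% for plausible truncated shapes; the extremes examined give 25% and 52%. About 80% power becomes about 63% in a two-arm contrast at an assumed two-sided alpha of 0.10.

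A reader might infer a threat to the main result. There is none: Sections 9.1 and 9.4.4 confine multiplicity control to three hypotheses, and the subgroup analyses lie outside them. If the SAP already contains continuous interactions, the point is closed.

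**What to change.** Keep all listed subgroups, including the eGFR split at 60, for display. Add to the SAP a supportive model for baseline sUA, and likewise for eGFR, log NT-proBNP, log UACR and age:

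- Extend the primary model with the centred continuous baseline value and its interactions with week, treatment and treatment by week, so that the effect can be read at Week 34. For log(UACR), the main effect and by-week term are already there.
- Report the change in the treatment ratio per unit of the baseline measure, with its confidence interval, for the main comparisons.
- Check linearity with a quadratic term or a spline, and show the categorical results beside it.
- Label the analyses as supportive and outside the testing hierarchy.

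The cost is a few lines of SAP text and one extra model per variable, with no new data and no change to the confirmatory tests. The drawback is the linearity assumption, which the check and the retained categories make visible.

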9.4.3 Safety analyses

All safety analyses will be performed on the Safety Population.

The assessment of safety will be based on the analyses of AEs, vital signs, ECGs and laboratory evaluations.

All safety data will be summarised by treatment group based on the treatment received.

The number and percent of patients with at least one AE will be summarised for each treatment group, including summaries of AEs, SAEs, and AEs leading to discontinuation. Summaries will include the number of subjects with events by system organ class and preferred term. The incidence of laboratory abnormalities, to be defined in the SAP, will be summarised for each treatment group. Values and changes from baseline at each scheduled time point for clinical laboratory parameters and vital signs, including blood pressure and heart rate, will be summarised by treatment group using descriptive statistics. Additional analyses of creatinine will be specified in the SAP. The normality/abnormality of ECG tracings, as determined by the investigator, will be summarised by shift tables overall and by ECG tracing at baseline.

9.4.4 Methods for multiplicity control

The experiment-wise Type I error will be controlled at 10% by hierarchical testing of the hypotheses in Section 9.1. No other comparisons will be adjusted for multiplicity.

9.5 Interim analyses

Two interim analyses will be performed to support internal decisions of the programme development. No multiplicity adjustment is planned for the interim analyses because there is no provision to stop the trial early at the interim analyses to claim efficacy.

These interim analyses will be conducted by an independent team who are not involved in the conduct of the study. A communication plan will be developed to explain who will review the results from interim analyses. All necessary steps will be taken to ensure the integrity of the trial by keeping the study team blinded throughout the study.

The first interim analysis will be performed no later than when 90% of subjects have completed 12 weeks of treatment after titration (Visit 7). The second interim analysis will be conducted after all subjects complete 26 weeks of treatment after titration (Visit 8). The scope of data analysis will be specified in a SAP.

11 SUPPORTING DOCUMENTATION AND OPERATIONAL CONSIDERATIONS

Appendix A Regulatory, ethical and study oversight considerations

A 1 Regulatory and ethical considerations

This study will be conducted in accordance with the protocol and with the following:

- Consensus ethical principles derived from international guidelines including the Declaration of Helsinki and Council for International Organisations of Medical Sciences (CIOMS) International Ethical Guidelines
- Applicable International Conference of Harmonisation (ICH) Good Clinical Practice (GCP) Guidelines
- Applicable laws and regulations

The protocol, protocol amendments, ICF, Investigator Brochure, and other relevant documents (eg, advertisements) must be submitted to an Institutional Review Board/Institutional Ethics Committee (IRB/IEC) by the investigator and reviewed and approved by the IRB/IEC before the study is initiated.

Any amendments to the protocol will require IRB/IEC approval before implementation of changes made to the study design, except for changes necessary to eliminate an immediate hazard to study patients.

The investigator will be responsible for the following:

- Providing written summaries of the status of the study to the IRB/IEC annually or more frequently in accordance with the requirements, policies, and procedures established by the IRB/IEC
- Notifying the IRB/IEC of SAEs or other significant safety findings as required by IRB/IEC procedures
- Providing oversight of the conduct of the study at the site and adherence to requirements of 21 CFR, ICH guidelines, the IRB/IEC, European regulation 536/2014 for clinical studies (if applicable), and all other applicable local regulations

The study will be performed in accordance with the AstraZeneca policy on Bioethics and Human Biological Samples.

A 2 Financial disclosure

Investigators and sub-investigators will provide the sponsor with sufficient, accurate financial information as requested to allow the sponsor to submit complete and accurate financial certification or disclosure statements to the appropriate regulatory authorities. Investigators

are responsible for providing information on financial interests during the course of the study and for 1 year after completion of the study.

A 3 Informed consent process

The investigator or his/her representative will explain the nature of the study to the patient or his/her legally authorised representative and answer all questions regarding the study.

Patients must be informed that their participation is voluntary. Patients or their legally authorised representative will be required to sign a statement of informed consent that meets the requirements of 21 CFR 50, local regulations, ICH guidelines, Health Insurance Portability and Accountability Act (HIPAA) requirements, where applicable, and the IRB/IEC or study centre.

The medical record must include a statement that written informed consent was obtained before the patient was enrolled in the study and the date the written consent was obtained. The authorised person obtaining the informed consent must also sign the ICF.

Patients must be re-consented to the most current version of the ICF(s) during their participation in the study.

A copy of the ICF(s) must be provided to the patient or the patient's legally authorised representative.

If applicable, a separate informed consent will be submitted to the Ethical Committee for procedures concerning the MRI test persons that are scanned to ensure the correct implementation of imaging methods.

Patients who are re-prescreened are required to sign a new brief ICF. The brief ICF is used to obtain patient consent for sUA, eGFR, and UACR assessments. Patients who are rescreened are required to sign a new full ICF. The full ICF is the master ICF for the study.

CCI

A 4 Data protection

Each patient will be assigned a unique identifier by the sponsor. Any patient records or data sets transferred to the sponsor will contain only the identifier; patient names or any information which would make the patient identifiable will not be transferred.

The patient must be informed that his/her personal study-related data will be used by the sponsor in accordance with local data protection law. The level of disclosure must also be explained to the patient.

The patient must be informed that his/her medical records may be examined by Clinical Quality Assurance auditors or other authorised personnel appointed by the sponsor, by appropriate IRB/IEC members, and by inspectors from regulatory authorities.

A 5 Committees structure

The safety of all AstraZeneca clinical studies is closely monitored on an on-going basis by AstraZeneca representatives in consultation with Patient Safety. Issues identified will be addressed; for instance, this could involve amendments to the Clinical Study Protocol and letters to investigators.

Data monitoring committee (DMC)

An independent DMC will be appointed and will report to AstraZeneca and the CRO. The DMC will be responsible for ensuring patient safety by assessing the safety of the IP during the study, and for reviewing the overall conduct of the study. The DMC will have access to the individual treatment codes and be able to merge these with the collected study data while the study is ongoing.

A DMC charter will be prepared to detail precise roles and responsibilities and procedures to ensure maintenance of the blinding and integrity of the study in the review of accumulating data and interactions with AstraZeneca and the CRO.

Clinical event adjudication (CEA)

The role of the CEA is to independently review, interpret and adjudicate potential CV events that are experienced by the patients. CV events will be identified preliminarily by the investigators, and also by AZ personnel, CRO personnel or in the CEA process as specified in the CEA charter. The CEA member/s will not have access to individual treatment codes for any patient or clinical efficacy endpoint and safety event. The precise responsibilities and procedures applicable for CEA will be detailed in the CEA charter.

A 6 Dissemination of clinical study data

A description of this clinical trial will be available on http://astrazenecaclinicaltrials.com and http://www.clinicaltrials.gov as will the summary of the study results when they are available. The clinical trial and/or summary of study results may also be available on other websites according to the regulations of the countries in which the study is conducted.

A 7 Data quality assurance

All patient data relating to the study will be recorded on printed or electronic CRF unless transmitted to the sponsor or designee electronically (eg, laboratory data). The investigator is responsible for verifying that data entries are accurate and correct by physically or electronically signing the CRF.

The investigator must maintain accurate documentation (source data) that supports the information entered in the CRF.

The investigator must permit study-related monitoring, audits, IRB/IEC review, and regulatory agency inspections and provide direct access to source data documents.

The sponsor or designee is responsible for the data management of this study including quality checking of the data.

Study monitors will perform ongoing source data verification to confirm that data entered into the CRF by authorised site personnel are accurate, complete, and verifiable from source documents; that the safety and rights of patients are being protected; and that the study is being conducted in accordance with the currently approved protocol and any other study agreements, ICH GCP, and all applicable regulatory requirements.

Records and documents, including signed ICFs, pertaining to the conduct of this study must be retained by the investigator for 15 years after study completion unless local regulations or institutional policies require a longer retention period. No records may be destroyed during the retention period without the written approval of the sponsor. No records may be transferred to another location or party without written notification to the sponsor.

A 8 Source documents

Source documents provide evidence for the existence of the patient and substantiate the integrity of the data collected. Source documents are filed at the investigator's site.

Data reported on the CRF that are transcribed from source documents must be consistent with the source documents or the discrepancies must be explained. The investigator may need to request previous medical records or transfer records, depending on the study. Also, current medical records must be available.

All information in original records and certified copies of original records of clinical findings, observations, or other activities in a clinical study necessary for the reconstruction and evaluation of the study are defined as source documents. Source data are contained in source documents (original records or certified copies).

A 9 Study and site start and closure

The study start date is the date on which the clinical study will be open for recruitment of participants.

The first act of recruitment is the first site deemed "ready to enrol" and will be the study start date.

The sponsor designee reserves the right to close the study site or terminate the study at any time for any reason at the sole discretion of the sponsor. Study sites will be closed upon study completion. A study site is considered closed when all required documents and study supplies have been collected and a study-site closure visit has been performed.

The investigator may initiate study-site closure at any time, provided there is reasonable cause and sufficient notice is given in advance of the intended termination.

Reasons for the early closure of a study site by the sponsor or investigator may include but are not limited to:

- Failure of the investigator to comply with the protocol, the requirements of the IRB/IEC or local health authorities, the sponsor's procedures, or GCP guidelines
- Inadequate recruitment of participants by the investigator
- Discontinuation of further study intervention development

If the study is prematurely terminated or suspended, the sponsor shall promptly inform the investigators, the IECs/IRBs, the regulatory authorities, and any CRO(s) used in the study of the reason for termination or suspension, as specified by the applicable regulatory requirements. The investigator shall promptly inform the participants and should ensure appropriate participant therapy and/or follow-up.

Participants from terminated sites will have the opportunity to be transferred to another site to continue the study.

A 10 Publication policy

The results of this study may be published or presented at scientific meetings. If this is foreseen, the investigator agrees to submit all manuscripts or abstracts to the sponsor before

submission. This allows the sponsor to protect proprietary information and to provide comments.

The sponsor will comply with the requirements for publication of study results. In accordance with standard editorial and ethical practice, the sponsor will generally support publication of multicentre studies only in their entirety and not as individual site data. In this case, a coordinating investigator will be designated by mutual agreement.

Authorship will be determined by mutual agreement and in line with International Committee of Medical Journal Editors authorship requirements.

